10.1 Clinical Course

Patients will be examined by oncologists at Memorial Hospital and have laboratory and radiographic studies performed as outlined in the above table. As this is a pilot study primarily concerned with effect of injection of sLe^a on immune response, intensive clinical follow-up at Memorial Hospital will not be required. However, if feasible, patients who remain clinically stable will be asked to return to Memorial Hospital every 3 months for a history and physical examination and laboratory studies.

The patient and their primary oncologist will be notified of all CTC results. These results are for research purposes and will not be used during the study to alter clinical care.

10.2 Immunologic Response

Serological response: Three 10 ml red top tubes will be drawn before the first injection, before each subsequent injection and also during weeks 5, 9, 13 and 23. Sera will be evaluated for reactivity against sLe^a in ELISA and/or immunoprecipitation-western blot assays. These assays detect antibodies against sLe^a and confirm identity of the reaction. If serologic reactivity is detected, then additional blood (~10ml) may be drawn at later times after the injections are completed to determine the duration of this response (every 3 months if feasible). An extra 100ml of heparinized blood may be obtained once during the course of immunizations depending on the serologic response in individual patients at the principal investigators discretion, for hybridoma production. This will be used for evaluation of the B-cell response to vaccination at the clonal level by establishment of monoclonal antibodies. This will be performed in collaboration with MabVax Therapeutics, Inc., (San Diego, CA). It will make possible more detailed analysis of the most immunogenic epitopes on sLe^a and more detailed comparison of the avidity of the induced IgG and IgM antibodies than is possible with sera.

T cell response will not be evaluated since this is a carbohydrate antigen and significant T cell response is not anticipated. The immune response analyses will be conducted in the laboratory of [name] under [name] supervision.

10.3 Circulating Tumor Cell Methodology

Epithelial cell adhesion molecule (EpCAM) is used to concentrate circulating epithelial tumor cells from a 7.5 ml peripheral blood specimen. A semi-automated system called CellSearch, uses EpCAM antibody-based immunomagnetic capture of epithelial cells to identify and isolate circulating tumor cells (CTC).

Immunomagnetically captured CTCs are stained and enumerated using specially prepared buffers and three immunofluorescent markers: DAPI to detect cells with intact nuclei; Cytokeratin-PE to detect epithelial cells; and CD-45-APC to detect leukocytes. CTCs are defined as DAPI(+), CK-PE(+) and CD-45(-) cells. Digitally archived images of candidate CTCs meeting these criteria also must meet standardized morphologic inspection.

11.0 TOXICITIES/SIDE EFFECTS

In our earlier breast cancer immunization trials, common toxicities included local skin reactions at the injection sites, flu-like symptoms (ie, fever, fatigue, myalgias, arthralgias), and less frequent symptoms such as pruritis, rashes, diarrhea, nausea and vomiting. These symptoms were transient and usually of less than 5 days duration. In addition, minimal transient decreases in hematologic values, primarily white blood cell counts and lymphocyte counts were noted. It is unlikely that these fluctuations were due to the vaccine. Transient elevation in various laboratory values (ie glucose, liver enzymes) were observed and also thought unrelated to the vaccine.

Since the antigen in this injection is present on the surface of normal tissues, the theoretical possibility of a serious autoimmune reaction exists. In our previous breast cancer trials, there was no consistent evidence of an autoimmune reaction due to the immunization. Several episodes of hyperthyroidism or hypothyroidism have occurred on these trials. Patients were subsequently treated with radioactive I-131 or thyroid supplementation. It is unclear whether these events were related to the immunization. Therefore, the thyroid stimulating hormone level will be monitored pre therapy, during therapy and post therapy.

In addition, no definite evidence of autoimmunity has been observed in immunization trials in prostate or ovarian cancer at MSKCC (personal communication with [name] and [name]). Autoimmune reactions may be controlled by cessation of the immunization and anti-inflammatory medications. The symptoms would be dependent on the organs involved. These may include but are not limited to diarrhea, dyspnea, numbness, weakness, vaginal bleeding, inflammation of the breast or pancreas and blood in the stool. This autoimmunity is considered unlikely however, since cytotoxic T-cells and antibodies against various antigens found on breast cancer cells have been recognized in the peripheral blood of patients with breast cancer in the absence of any evidence for autoimmunity. Some patients have also demonstrated baseline antibody titers against various antigens used in our prior trials.

In MSKCC protocol 01-019 several episodes of transient asymptomatic elevation of the AST and ALT levels (grade 1-3) were observed. The finding was thought to be due to the GPI-0100 and we do not anticipate this toxicity on this trial using QS-21.

12.0 CRITERIA FOR THERAPEUTIC RESPONSE/OUTCOME ASSESSMENT

The primary endpoints of this trial are toxicity and immunologic response. Patients will have baseline imaging studies to assess the extent of the disease. However, patients will not routinely undergo followup imaging studies unless felt to be appropriate by their physician as standard of care.

12.1 Long Term Followup

Patients will be followed every 3 months if feasible following completion of the vaccine trial, until evidence of disease progression. Shorter time intervals between visits may be required, according to the standard of care for the patient's state of disease.

12.2 Evaluability

Efforts shall be made to account for all patients entered into the study during the evaluation of results. All patients will be considered evaluable for safety and immune response.

12.3 Clinical Response

Patients will be monitored for anti-tumor effect, although this is not a primary endpoint. Patients who have evidence of disease will be evaluated at week 19 or at the discretion of their physician. Responses will be categorized using RECIST response criteria as follows:

Complete Response (CR):

Target Response Criteria: The disappearance of all known disease and no new sites or disease related symptoms confirmed at least 4 weeks after initial documentation. All sites must be assessed, including non-measurable sites, such as effusions, or markers

Non-Target Response Criteria: Disappearance of all non-target lesions and normalization of tumor markers level confirmed at least 4 weeks after initial documentation.

Partial Response (PR):

Target Response Criteria: At least a 30% decrease in the sum of the longest diameters of target lesions, taking as a reference the baseline sum of the longest diameters confirmed at least 4 weeks after initial documentation. PR is also recorded when all measurable disease has completely disappeared, but a non-measurable component (i.e., ascites) is still present but not progressing.

Stable Disease (SD):

Target Response Criteria: Neither sufficient shrinkage to qualify for partial response nor sufficient increase to qualify for progressive disease.

Non-Target Response Criteria: Persistence of one or more non-target lesions and/or the maintenance of tumor marker level above the normal limits.

Progressive Disease (PD):

Target Response Criteria: At least a 20% increase in the sum of the longest diameters of target lesions, taking as reference the smallest sum of the longest diameters recorded since the treatment started; or the appearance of one or more new lesions; or the unequivocal progression of a non-target lesion.

Non-Target Response Criteria: Appearance of one or more non-target lesions and/or unequivocal progression of existing non-target lesions.

13.1 CRITERIA FOR REMOVAL FROM STUDY

Cessation of treatment

Therapy may be discontinued at any time due to severe unacceptable side effects, dose-limiting toxicities as defined, life-threatening events, patient's non-compliance with the defined treatment plan, the patient becomes pregnant or the patient's request to withdraw consent.

With evidence of recurrent disease or progression of disease, the patient's primary physician will be notified immediately by the protocol investigators. The decision regarding optimal therapy will be made by the patient and the primary physician. The patient may continue on study if the patient's primary physician feels it is acceptable and the only change in therapy is hormone therapy.

The following dose limiting toxicities as evaluated during weeks 1-21 will result in cessation of treatment:

- Grade 2 or greater autoimmune reactions
- Grade 2 or greater allergic reactions (excluding isolated fever and/or flushing)
- Grade 3 or greater toxicity of any kind (excluding grade 3 lymphopenia)

If any of these toxicities occur, no additional patients will be treated except following mutual agreement after discussion with the CBER IND review team.

14.0 BIOSTATISTICS

This is a pilot study designed to assess the safety and immunogenicity of immunization with sLe^a-KLH plus QS-21 in patients with high risk breast cancer. If immune responses are observed at the 100 mcg level of QS-21 then QS-21 will be escalated to the 150mcg level.

The immunization schedule comprises five injections administered during weeks 1,2,3,7 and 19. The primary endpoint of this trial is to evaluate immunological response to this single antigen and evaluate toxicity. Immunological response for a patient is defined as an antibody response of greater than 1:80 if baseline value was 0 and at least an increase of 8-fold if baseline value is greater than 0. Initially, three patients will be accrued to the study at a dose of 10 mcg of sLe^a. If safe, then ten patients will be accrued to the study at the full 30mcg sLe^a dose. If 6 or more of these 10 patients have an immune response at any time point then an additional 10 patients may be accrued and receive sLe^a-KLH plus QS-21 (at 150mcg) during weeks 1, 7 and 19. This sample size is chosen to minimize the total number of patients who need to be immunized to identify a promising agent with a probability of an immunological response greater than 50% in a series of immunization trials. The error rates of missing a promising agent or selecting a nonpromising agent are set to be at most 10%.³⁶

At the end of the trial a qualitative assessment of the number of responses and frequency of toxicities will be made to determine which dose of QS-21 will be carried forward in future studies.

Severe toxicities are not anticipated. Toxicities will be tabulated according to the NCI CTC version 3.0. Any grade 3 or greater toxicity (excluding grade 3 lymphopenia) or grade 2 or greater allergic/immunologic toxicity (except isolated fever and/or flushing) will result in removal of the patient from the study. Since the above listed toxicities are unexpected, any event of this sort will result in suspension of the study pending further investigation. Descriptive statistics summarizing the antibody responses will be provided for each patient. The length of the study will be approximately 1-2 years.

Circulating tumor cells (CTC) will be evaluated in an exploratory manner to determine whether CTC can be detected in this patient population at baseline and if so whether there is evidence of a decline in those patients who have an immune response.

Severe toxicity is not anticipated. Frequencies of all toxicities will be recorded. We plan to accrue approximately 1-2 patients per month and therefore accrual should be completed in 10 months.

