2.1 OBJECTIVES AND SCIENTIFIC AIMS

The primary objectives of this trial are to determine the following endpoints after injection with sLe^a-KLH plus QS-21:

- Safety
- The IgG and IgM antibody response to sLe^a and breast cancer cells expressing this antigen

The secondary objective of this trial is to monitor the presence of circulating tumor cells (CTC) prior to, during and after injection with sLe^a-KLH plus QS-21.

Clinical response will be monitored but will not be an endpoint. As part of standard care, patients on this trial will be followed for progression of disease. It is unknown how many patients will enroll with evidence of disease. Therefore, we will report any responses that are observed for these patients in a purely descriptive manner (see section12). This is consistent with the pilot vaccine trials we have previously conducted.

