3.4 Rationale for Evaluation of sialyl Lewis^a (sLe^a)-KLH plus QS-21

The carbohydrate antigen sLe^a is the antigen recognized by monoclonal antibody 19.9 and is commonly expressed on breast cancer cells. In a study of 43 breast cancer patients with infiltrating ductal carcinoma it was found in about 79% of samples.²⁴ There was high expression in patients with greater node involvement. sLe^a may be a ligand for endothelial leukocyte adhesion molecule and therefore have an impact on metastatic potential.

sLe^a is expressed primarily as a glycolipid on the surface of cancer cells. We are preparing a polyvalent vaccine for evaluation in patients with breast cancer. It contains four antigens expressed on mucins (MUC1, Tn, sTn and TF) and three antigens expressed as glycolipids (GM2, globo H and Lewis Y). There are advantages to glycolipid antigens including greater susceptibility to activation of complement in the presence of antibodies and greater induction of complement mediated cytotoxicity, as recently described.^{24a} We have recently learned that Lewis Y is poorly immunogenic, inducing antibodies in fewer than 30% of vaccinated patients. If sLe^a proves immunogenic in this trial, we plan to replace Lewis Y in the polyvalent construct with sLe^a.

In this protocol, we propose to evaluate a construct containing the antigen sLe^a for toxicity and immunogenicity. If the injections are well tolerated and immunogenic, then sLe^a will be incorporated into a future polyvalent construct. This is the first time that sLe^a is being evaluated in humans.

Our prior breast cancer immunization protocols used 100 mcg of QS-21. The greatest toxicity primarily occurred during weeks 2 and 3. In an attempt to increase the immunogenicity of the construct, if six or more of the initial ten patients demonstrate an immune response against sLe^a and the injection is well tolerated, the dose of QS-21 will be increased to 150 mcg during weeks 1, 7 and 19 in a second group of 10 patients. We do not anticipate significant increases in toxicity as prior evaluations of 200 mcg of QS-21 were tolerated.

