4.1 OVERVIEW OF STUDY DESIGN/INTERVENTION

4.2 Design

This is a pilot study designed to assess the safety and immunogenicity of a sLe^a-KLH plus QS-21 construct in patients with metastatic breast cancer. Initially 3 patients will be accrued to the study at a 10 mcg dose of sLe^a. If safe, then 10 patients will be accrued at the 30 mcg dose of sLe^a. If 6 or more of these 10 patients have an immune response at any time point then an additional 10 patients will be accrued and injected with a higher dose of QS-21. Toxicities will be monitored during the study. Patients will be instructed to complete a patient diary and document any side effects.

Patient blood samples will be evaluated for an IgG and IgM antibody response to sLe^a and breast cancer cells expressing this antigen. Immunological response for a patient is defined as an antibody response of greater than 1:80 if baseline value was 0 and at least an increase of 8-fold if baseline value is greater than 0. Patient blood samples will also be monitored for the presence of circulating tumor cells pre study and then during weeks 5, 13, and 23.

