10.0 EVALUATION DURING TREATMENT/INTERVENTION

The study evaluation will include parameters to assess the safety of the injections as well as assessments of immunity to sLe^a (Appendix A). Interval safety assessments will include the „Patient Diary“ (Appendix B). Patients will be provided with Appendix A and B. Long term followup will also be maintained to assess toxicity. Although not a primary endpoint, patients will be monitored for any evidence of an anti-tumor effect. Imaging to assess extent of disease will be performed at baseline, then as appropriate for clinical circumstances. Patients with metastatic disease are often evaluated with imaging every 3 months as standard of care. Clinical benefit will also be assessed by physical examination and biochemical studies as outlined below.

SUMMARY TABLE OF EVALUATION

STUDY WEEK VACCINATION	Pre	1	2	3	5	7	9	13	19	23	q3 months ^g
Clinical:											
History	X	X				X		X	X	X	X
Physical Exam	X	X				X		X	X	X	X
CBC w/ Diff	X					X		X	X		
COMP ^b	X				X	X		X	X	X	
CEA, CA153	X										X ^f
TSH	X						X				X
Urinalysis	X										
Pathology Review	X										
Pregnancy Test	X ^a										
Rectal/Hemoccult	X										
Imaging:											
Bone scan	X									X ^f	
CT Scans	X									X ^f	
Response Assessments ^d									X ^f	X ^f	
Anti-sLe ^a											
Immunity:											
Serology (3 RTT)	X	X ^e	X ^e	X ^e	X	X ^e	X	X	X ^e	X	X
CTC Assay	X				X		X		X		X

^a Within 2 weeks of the first injection for a premenopausal patient..

^b Includes total bilirubin, AST, ALT, Sodium, Potassium, Chloride, CO₂, Calcium, Glucose, Total Protein, Albumin, Alkaline Phosphatase, Creatinine, BUN, Bilirubin.

^c Patients may be asked to obtain tissue blocks from previous diagnostic/therapeutic procedures.

^d Overall response assessment includes the measurement of tumor by non-imaging studies such as physical exam.

^e Blood must be drawn before administration of vaccine at week 1,2, 3, 7 and 19. An extra 100ml of heparinized blood may be drawn once (during weeks 9-23) during the course of immunizations depending on the serologic response in individual patients, at the principal investigators discretion, for evaluation of the immune response at the clonal level by hybridoma production.

^f These studies will be performed as standard of care if deemed appropriate by the patient's physician.

^g If feasible, a history and physical examination and serology will be obtained every 3 months until evidence of disease progression.

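### Is the tumour-cell part of the antibody objective left without data because the assay and endpoint sections name only sLe^a?

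*Combined protocol and SAP*

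**What the plan says.** The second primary objective in section 2.1 has two targets: "The IgG and IgM antibody response to sLe^a and breast cancer cells expressing this antigen". Section 4.2 turns this into a commitment: "Patient blood samples will be evaluated for an IgG and IgM antibody response to sLe^a and breast cancer cells expressing this antigen". The next sentence of 4.2 gives the responder rule, a titre above 1:80 from a zero baseline or at least an eightfold rise otherwise. It names neither a target nor an isotype.

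Later sections are narrower. Section 10.0 describes the evaluation as covering safety "as well as assessments of immunity to sLe^a", and its schedule has a single serology row. On methods, section 10.2 says: "Sera will be evaluated for reactivity against sLe^a in ELISA and/or immunoprecipitation-western blot assays". It adds: "These assays detect antibodies against sLe^a and confirm identity of the reaction". Section 14.0 gives the endpoint as: "The primary endpoint of this trial is to evaluate immunological response to this single antigen and evaluate toxicity". It repeats the responder rule, again without a target, and promises descriptive summaries of the antibody responses patient by patient.

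On blood collection, section 10.2 says: "Three 10 ml red top tubes will be drawn before the first injection". The same draw is repeated before each later injection and in weeks 5, 9, 13 and 23. Section 4.3 schedules blood for immune response at a pre-study visit and in the same weeks.

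**The concern.** An objective listed as primary should lead to a measurement, a criterion and a summary. Sections 2.1 and 4.2 name two targets, but the sections on assays, evaluation and statistics speak of sLe^a alone. No section names a cell-binding assay or a target cell line. Section 10.2 also joins its two methods with and/or, so ELISA alone would satisfy it.

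The cell readout is of scientific interest. Section 3.4 favours glycolipid antigens partly for "greater induction of complement mediated cytotoxicity", an effect that needs antibody bound to cells, and plans to put sLe^a in place of Lewis Y in the polyvalent construct if it proves immunogenic. If no cell data were produced, that choice would rest on binding to the antigen alone. If a cell assay were specified late, its line, week and cut-off could be chosen with the sLe^a titres already known.

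**Working it through.** The question is mainly one of text, so the first step sets out what a cell readout needs and where the plan supplies it. The later steps check whether anything numerical depends on the gap.

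**1. Elements of a cell readout**

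| Element | Where found |
|---|---|
| Commitment to test | Section 4.2, both targets named |
| Serum | Section 10.2, three 10 ml tubes per draw |
| Sampling weeks | Sections 4.3 and 10.2 |
| Positivity rule | Section 4.2, directly after the two-target sentence; no target restriction |
| Summary | Section 14.0, descriptive, per patient; no target restriction |
| Named assay for cells | Not given |
| Named cell line | Not given |

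Five of the seven elements are present, although the positivity rule and the summary are general statements rather than cell-specific ones. The two that are missing are laboratory detail.

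Serum is not limiting. There are 5 pre-injection draws (weeks 1, 2, 3, 7, 19) plus 4 others (weeks 5, 9, 13, 23), which makes 9 draws. At 30 ml each, that is 270 ml per patient.

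**2. Does the wording of 14.0 exclude cells?** Sections 3.3, 3.4 and 4.3 repeatedly set one-antigen constructs against polyvalent ones. Read in that light, the single-antigen phrase describes the vaccine. Cells chosen because they express sLe^a present that same antigen, so the phrase does not have to rule them out.

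**3. Does the 6-of-10 rule depend on the target?** The chance of passing is the sum over k = 6 to 10 of C(10,k) p^k (1−p)^(10−k).

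- p = 0.30: 0.047
- p = 0.50: (210 + 120 + 45 + 10 + 1)/1024 = 386/1024 = 0.377
- p = 0.70: 0.850

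Section 14.0 states error rates of at most 10%. These cannot be reproduced, because they come from a cited method for a series of trials whose inputs the plan does not give. They are not in dispute here.

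The target would matter if it were open. Take a response rate of 0.50 to each target and, as an extreme assumption, independence between targets:

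- either target counts: p = 1 − 0.5² = 0.75, chance of passing 0.922
- both targets required: p = 0.5² = 0.25, chance of passing 0.020

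Real responses would be correlated and the spread smaller. The target is not open in any case: section 3.4 states the rule as a response against sLe^a among the initial ten patients. The single-target figures apply.

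**4. What could a cell readout show?** Suppose exactly 6 of 10 respond to sLe^a and the cell result is counted among those six. Exact (Clopper-Pearson) 95% intervals are:

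- 0 of 6: upper limit 1 − 0.025^(1/6) = 0.459, so 0% to 46%
- 3 of 6: 12% to 88%
- 6 of 6: lower limit 0.025^(1/6) = 0.541, so 54% to 100%

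Only the extremes can be told apart. These outcomes are illustrations; the documents give no rate of cell binding.

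**5. What would a full written specification cost?** Take sera at baseline and weeks 9 and 23, a positive and a negative cell line, and two isotypes.

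- 13 patients (3 + 10): 3 × 13 = 39 sera; 39 × 2 × 2 = 156 determinations
- 23 patients (3 + 10 + 10): 3 × 23 = 69 sera; 69 × 2 × 2 = 276 determinations

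This assumes that every patient reaches week 23. It would also use only 2 of the 8 draws that follow the first injection, whereas response to sLe^a may be counted at any visit. A patient who responded in week 5, 13 or 19 could then be recorded as cell-negative for reasons of timing.

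**The case for a change.** The strongest contrary argument is one of proportion. Circulating tumour cells are a secondary, exploratory measure, yet they have a method section (10.3), sampling weeks and their own paragraph in 14.0. Part of a primary objective has only a general commitment. A sentence of intent in 4.2 is not a method, and the section that does give methods leaves that target out. Immunoprecipitation might use cell material, but 10.2 does not say so. The background in section 3.2.2 also reports antigen titres and tumour-cell titres as separate results, which suggests that one does not stand in for the other.

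Part of this stands. The sections are uneven, and a reader of 10.2 alone would not learn how cell reactivity will be measured. Other parts carry less weight. The example in 3.2.2 comes from immunised mice. The complaint about Lewis Y in 3.4 is that it induced antibodies in fewer than 30% of vaccinated patients, so immunogenic there is most naturally read as antibody induction. The complement argument explains the interest in glycolipids and is not set as a criterion for this trial. A late choice of cell line or cut-off is possible, but nothing in the plan says it will happen, and no decision rule would use the result.

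**Conclusion.** The mismatch between sections 2.1 and 4.2 on one side and 10.0, 10.2 and 14.0 on the other is real, but it is a gap in laboratory detail that the investigators would fill sensibly. It does not follow that the trial would end without cell data: the commitment, the serum and the schedule are there, together with a general responder rule and a promise of descriptive reporting.

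The effect on the design is nil. The 6-of-10 rule, the 13 or 23 patients and the safety rules are the same whether or not a cell assay is written down. Deleting the cell wording would only trim text. Specifying the assay in full would add 156 to 276 determinations under the scheme costed above, and choices of week and control line that the documents do not support, for a result that stays descriptive.

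This conclusion rests on two readings: that 4.2 is a genuine commitment to test against cells, and that 3.4 fixes sLe^a as the target of the 6-of-10 rule. The text supports both. If cell reactivity were to enter the rule, step 3 shows that the target would have to be stated.

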The potential benefits of this study include generation of an anti-tumor response by stimulation of the immune system. While it is possible that this treatment will result in shrinkage of breast cancer tumors, delay a recurrence or decrease the risk of progression, it is not known whether these effects will occur. If this study demonstrates that the sLe^a-KLH conjugate is safe and immunogenic, it will be incorporated into a polyvalent vaccine that will be evaluated in high risk breast cancer patients for clinical benefit.

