4.3 Intervention

Patients will receive sLe^a-KLH plus QS-21 subcutaneously during weeks 1,2,3,7 and 19. The first 3 patients will receive a 10 mcg dose of sLe^a and subsequently all patients will receive a 30 mcg dose of sLe^a. The dose of QS-21 is 100 mcg for the initial 13 patients. If immune responses are observed at the 100 mcg level of QS-21 then the dose of QS-21 will be escalated to 150 mcg, in a subsequent group of patients during weeks 1, 7 and 19. Blood samples will be obtained pre study and during weeks 1,2,3,5,7,9,13, 19 and 23 to assess for immune response.

sLe^a is one of multiple antigens found on breast cancer cells. Data from this trial will be used to determine whether the sLe^a antigen will be included in a future polyvalent construct. Ultimately we plan a multicenter randomized clinical trial to assess potential clinical benefit of immunization with a polyvalent construct in high risk breast cancer patients.

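### Does the plan lack a rule for selecting sLe^a, leaving its 10% error rates attached to no decision?

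*Combined protocol and SAP*

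**What the plan says.** Section 14.0 (Biostatistics) gives the rule: "If 6 or more of these 10 patients have an immune response at any time point then an additional 10 patients may be accrued", with QS-21 at 150 mcg during weeks 1, 7 and 19. The next sentence says that the sample size was chosen to "identify a promising agent with a probability of an immunological response greater than 50% in a series of immunization trials". The sentence after that reads "The error rates of missing a promising agent or selecting a nonpromising agent are set to be at most 10" percent, and cites a methodological paper on sample size for a series of pilot trials (reference 36). Section 14.0 then provides for a qualitative end-of-trial assessment of responses and toxicities "to determine which dose of QS-21 will be carried forward in future studies".

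The use of the results is described elsewhere. Section 4.3: "Data from this trial will be used to determine whether the sLe^a antigen will be included in a future polyvalent construct". Section 3.4: "If sLe^a proves immunogenic in this trial, we plan to replace Lewis Y in the polyvalent construct with sLe^a", and "If this study demonstrates that the sLe^a-KLH conjugate is safe and immunogenic, it will be incorporated into a polyvalent vaccine". Section 3.4 also explains why Lewis Y is to be replaced: "Lewis Y is poorly immunogenic, inducing antibodies in fewer than 30% of vaccinated patients".

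**The concern.** An error rate is a property of a decision rule. Section 14.0 speaks of selecting or missing an agent, but wherever the 6-of-10 rule appears (Sections 1.0, 3.4, 4.2, 5.1.2 and 14.0) its stated consequence is the second QS-21 group. The sentences about the polyvalent construct require only that sLe^a be immunogenic and safe or well tolerated. They give no count, no denominator and no patient group.

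Two results then seem to have no agreed meaning. With 4 or 5 responders of 10, sLe^a falls short of the above-50% criterion but has a higher observed rate than the figure quoted for Lewis Y. With 6 of 10 in the first group and 3 of 10 in the second (9 of 20 overall), the first group passes but the combined result is below half. If the rule were truly open, the choice could be made after the data are seen, and the 10% would describe no identifiable decision.

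**Working it through.** **Inputs.** From Section 14.0: n = 10, cutoff 6, promising means a response probability above 50%, each error at most 10%. From Section 3.4: Lewis Y below 30%. The documents give no nonpromising design rate and no distribution of response rates across agents.

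**The plan's own figure.** With X ~ Binomial(10, p), the chance of passing is P(X ≥ 6), the sum over x = 6 to 10 of C(10,x) p^x (1−p)^(10−x).

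| True rate p | P(X ≥ 6) | P(X ≤ 5) |
|---|---|---|
| 30% | 4.7% | 95.3% |
| 40% | 16.6% | 83.4% |
| 50% | 37.7% | 62.3% |
| 60% | 63.3% | 36.7% |
| 70% | 85.0% | 15.0% |

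At p = 50% the two probabilities sum to 100%, so no cutoff keeps both errors within 10% right up to the boundary. For fixed rates, both are within 10% only if nonpromising means p of about 35.4% or less and promising means about 73.3% or more. The plan instead frames its errors over a series of trials, which suggests averaging over agents. With an assumed uniform distribution of p split at 50%, the gate's errors are 3.9% (false selection) and 8.4% (miss) as shares of all trials. Conditional on the true state they are 7.8% and 16.9%. The 10% can therefore be neither confirmed nor refuted from the documents, although one plausible reading meets it with the 6-of-10 rule.

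**Would another rule matter?** Three alternatives were tried. The two-group rules assume independent groups with the same p.

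| Rule | Forward at p = 40% | Forward at p = 60% |
|---|---|---|
| At least 6 of the first 10 | 16.6% | 63.3% |
| That, and at least 11 of 20 pooled | 7.8% | 57.8% |
| At least 6 of 10 in both groups | 2.8% | 40.1% |
| At least 4 of the first 10 | 61.8% | 94.5% |

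The chance of exactly 4 or 5 of 10 is 45.1% at p = 40%, 47.2% at 45% and 45.1% at 50%. The choice of rule would matter if it were open.

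**Is it open?** Within Section 14.0 the order is: the 6-of-10 rule, the purpose of that sample size (finding an agent above 50%), and the error rates of selecting or missing an agent. Six is the smallest count of 10 above 50%, and no other numerical rule in the section could carry those error rates. The alternatives have no source:

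- The 4-of-10 rule turns the Lewis Y figure into a threshold. Section 3.4 gives that figure as the reason for replacing Lewis Y, and does not set it as a standard for sLe^a.
- The pooled and both-groups rules mix patients on different QS-21 schedules. Section 14.0 uses the end-of-trial comparison only to choose the QS-21 dose. The equal-p assumption also sits badly with Section 3.4, where QS-21 is raised in the hope of a stronger response.

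**Can the 10% identify the rule?** No. With p ~ Beta(0.4, 0.4) and errors conditional on the true state, the gate gives 4.3%/9.6% (false selection/miss) and the pooled rule 2.2%/10.9%, so only the gate fits. With Beta(0.3, 0.3) the pooled rule gives 1.8%/8.8% and fits too. With Beta(0.1, 0.1) all four rules stay below 10%. These distributions are assumptions, so the reading rests on the text of Section 14.0 and not on the 10%.

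**The case for a change.** The strongest case for a change is that the plan itself claims formal error rates for selection, so calling the study a pilot is no excuse for leaving the rule to inference. Failing the gate is said only to mean no second group. It is not said to mean that sLe^a is dropped. Second-group patients receive the same 30 mcg of sLe^a, and response to this antigen is a primary endpoint, so a reader could reasonably ask whether their results count. One sentence would settle this at no cost in patients or conduct.

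Part of this stands. No sentence in the documents says in so many words that sLe^a is selected at 6 of 10, and the polyvalent wording carries no count. What does not follow is that the decision is undefined. The plan has one numerical criterion for a promising agent, placed beside the only rule that matches it, and on that criterion 4 or 5 of 10 does not qualify. The added sentence would repeat that rule. Restating the error definition and the assumed distribution of response rates would be helpful, but citing a published design for them is a legitimate reporting choice.

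**Conclusion.** No change follows. This is a gap in wording that an analyst would fill in the same way the section does: sLe^a counts as promising if at least 6 of the first 10 full-dose patients respond, and the second group informs the choice of QS-21 dose. Following the plan on that reading gives no wrong result. Sample size, gate and conduct are unaffected, and inclusion in a later construct also depends on safety (Section 3.4).

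The rule's selection probabilities, 4.7% at a true rate of 30% rising to 85.0% at 70%, are exact under a binomial model with independent patients. The large differences from other rules (2.8% to 61.8% at a true rate of 40%) depend on thresholds that the documents do not contain. The conclusion rests on reading the consecutive sentences of Section 14.0 together. It does not depend on verifying the 10%, which cannot be done without the distribution of response rates behind it.
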